Multi-center, two-arm, prospective, Phase II, open label, randomized controlled trial.

Study Population

Hospitalized COVID-19 patients fulfilling the inclusion and exclusion criteria, and admitted for care at COVID-19 management facilities in India will be eligible for inclusion in the trial.

Inclusion Criteria

1. Patients admitted with RT-PCR confirmed COVID-19 illness.
2. Age > 18 years
3. Written informed consent
4. Has any of the two
 - a. PaO₂/ FiO₂ <300
 - b. Respiratory Rate > 24/min and SaO₂ ≤ 93% on room air

Exclusion criteria

1. Pregnant women
2. Breastfeeding women

3. Known hypersensitivity to blood products
4. Receipt of Pooled Immunoglobulin in last 30 days
5. Critically ill patients:
 - a. P/F ratio <200 (moderate - severe ARDS)
 - b. Shock (Requiring Vasopressor to maintain a MAP \geq 65mmHg or MAP below 65)
6. Participating in any other clinical trial
7. Clinical status precluding infusion of blood products

Assessment of donor for eligibility

COVID-19 convalescent plasma will be collected from recovered individuals if they are eligible to donate blood. Considerations for assessment of donor for eligibility are outlined in the section on convalescent plasma.

Sample Size

For sample size calculation, we considered that given the standard of care, 18% of patients would succumb to COVID-19 infections.[5] We considered a relative effectiveness of 50% for sample size calculations. We calculated sample size using the PASS v11.0 software.[42]

Group sample sizes of 226 in the intervention group and 226 in the control group achieve 80% power to detect an absolute difference of -0.09 between the group proportions. The proportion of participants meeting the primary outcome in group one (the treatment group) is assumed to be 0.18 under the null hypothesis and 0.09 under the alternative hypothesis. The proportion of participants in group two (the control group) who meet the primary outcome is assumed to be 0.18 based on current evidence.[5] The test statistic used is the two-sided Z test with pooled variance. The significance level of the test was targeted at 0.05, with a power of 0.8.

Primary Outcomes

The primary outcome is a composite measure of the avoidance of -

1. Progression to severe ARDS (P/F ratio <100) and
2. All-cause Mortality at 28 days

Secondary Outcomes

1. Time to symptom resolution
 - a. Fever
 - b. Shortness of Breath
 - c. Fatigue
2. Hospital length of stay
3. Change in SOFA pre and post transfusion

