Randomization	x							
Convalescent Plasma Infusion			x					
Vital signs	x	x	xxxxx ¹	x	x	x	x	x
Physical examination	x		x	x		x		x
Concomitant medications		x	x					
Adverse event monitoring			x	x	x	x	x	x
Lab Investigations								
CBC and CMP		x		x		x	x	
SARS-CoV-2 RT-PCR		x			x	x	x	
SARS-CoV-2 antibody		x		x	x	x	x	
Blood for testing and archiving		x		x	x	x	x	
Imaging		x		x				x
Others	As clinically indicated							

1 Vital signs need to be tested immediately prior to infusion, within 15 minutes after initiation of infusion, at the completion of infusion and within 1 hour of end of infusion

Convalescent plasma:

Eligibility of Donor

Potential donors will include the following[39]:

- Prior diagnosis of COVID-19 documented by a laboratory test and
- Complete resolution of symptoms and at least one negative lab test for COVID-19 at least 28 days prior to donation (as per NBTC guidelines after COVID -19 pandemic for donor selection). If plasma is collected prior to 28 days after full recovery from illness, then confirmation of the resolution of the infection should be obtained through demonstration of two non-reactive Nucleic Acid Tests (NAT) for SARS-CoV-2 performed at an interval of at least 24 hours on nasopharyngeal swabs.
- These individuals will be contacted telephonically and explained the details of the study and their extent of participation. They will be encouraged to visit the main blood bank for further evaluation towards eligibility for blood donation. If requested, they will be provided transport for the same.

Recruitment of Donor

At the time of discharge, all recovered COVID-19 patients will be counselled. They will be motivated towards donation of convalescent plasma after 28 days of symptom free period and its probable beneficial effects in the management of COVID-19 patients. Such patients will be briefed in detail regarding their extent of participation in the study. Later on, these individuals will be contacted telephonically on Post discharge Day 25. They will be encouraged to visit the Blood Bank for further evaluation towards eligibility for blood donation. If need arises, the participant will be provided conveyance for facilitating transport.

Donor eligibility criteria

The following eligibility criteria will be applied towards potential donors:

1. Only males and nulliparous female donors of weight > 55 kgs will be included.

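### Severe ARDS is one of two primary-outcome components, but the schedule fixes no post-randomisation measurement of PaO2/FiO2, so in this open-label trial its detection can differ by arm

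*Protocol*

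**What the plan says.** Under Primary Outcomes, the composite is the avoidance of two items: item 1, "Progression to severe ARDS (P/F ratio <100) and", is joined to item 2, "All-cause Mortality at 28 days". The 28-day limit is attached to the second item only. The Analysis Plan codes the composite as met or not met.

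Study Design describes a "Multi-center, two-arm, prospective, Phase II, open label, randomized controlled trial".

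The Study Procedures table has rows for symptoms, vital signs, physical examination, concomitant medications, adverse events, CBC and CMP, RT-PCR, antibody, "Blood for testing and archiving" and imaging. It has none for blood gas, PaO2, FiO2, P/F ratio or SOFA. The last row, Others, says "As clinically indicated". Vital signs are due at screening, at baseline, around the infusion and on days 1, 3, 7, 14 and 28. Their footnote sets timing ("Vital signs need to be tested immediately prior to infusion, within 15 minutes after initiation of infusion", then at completion and within an hour of the end) but does not say which signs are recorded.

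Infusion of Blood Products asks for particular attention to transfused patients during the infusion and for 24 hours afterwards. Controls have no matching instruction.

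**The concern.** Death will be known for almost everyone followed to day 28. A P/F ratio below 100 is known only if oxygenation was measured and recorded. The protocol fixes days for imaging and antibodies but not for the measurement that defines a primary event. When to take it is left to treating teams who know the allocation, at several centres.

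Two things are at stake. If detection differs by arm, the comparison of composite rates is biased even when plasma does nothing. If detection is incomplete but equal, the type I error holds and power is lost. A later analysis plan can say how to classify missing measurements, but it cannot recover oxygenation that was never recorded.

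**Working it through.** **Step 1. The plan's own figure.** Inputs from Sample Size: 0.18 against 0.09, two-sided 0.05, power 0.8, pooled-variance Z test. With mean proportion 0.135:

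n = [1.960·√(2·0.135·0.865) + 0.842·√(0.09·0.91 + 0.18·0.82)]² / 0.09² = (0.947 + 0.403)² / 0.0081 ≈ 225.1, so 226 per arm, as stated.

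Power at 226 per arm is 80.15% by the normal approximation and 81% by exact enumeration of the same test. The sample size is not in question.

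**Step 2. Model for incomplete detection.** Let T be the true composite rate, s the share of events that are non-fatal ARDS only, and d the proportion of those that are detected. The model treats an undetected event as no event, which is an assumption.

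Observed rate = T(1 − s) + T·s·d

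T = 0.18 comes from the protocol. The values of s and d do not. The protocol gives no split of events, and its 18% is introduced as a proportion dying before it is used for the composite.

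**Step 3. No true effect.** T = 0.18 in both arms, 226 per arm, exact enumeration of the pooled Z test, nominal 2.5% per side.

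| s | d control | d plasma | Observed control | Observed plasma | False benefit | False harm |
|---|---|---|---|---|---|---|
| any | 100% | 100% | 0.180 | 0.180 | 2.5% | 2.5% |
| 50% | 90% | 80% | 0.171 | 0.162 | 4.5% | 1.35% |
| 50% | 90% | 70% | 0.171 | 0.153 | 7.5% | 0.7% |
| 50% | 70% | 90% | 0.153 | 0.171 | 0.7% | 7.5% |
| 25% | 90% | 70% | 0.1755 | 0.1665 | 4.4% | 1.36% |

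Worked example, third row: control 0.09 + 0.09·0.9 = 0.171; plasma 0.09 + 0.09·0.7 = 0.153. The apparent difference is 1.8 percentage points.

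**Step 4. Equal under-detection with a true effect.** s = 50% and d = 70% in both arms. Control: 0.09 + 0.09·0.7 = 0.153. Plasma: 0.045 + 0.045·0.7 = 0.0765. Exact power falls from 81% to 73%, and the false-positive rate stays at about 2.5% per side.

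**The case against.** The strongest reply is that the schedule is not a full list of what is captured. Hospital stay, duration of ventilation and vasopressor use have no rows either, and Types of Data names medical records and laboratory reports as sources. Patients are in hospital, ARDS is to be managed under the same named guideline in both arms, and those nearing a P/F ratio of 100 would often have a blood gas in routine care. This stands in part. It rules out saying that the component is captured only at a clinician's whim, and it probably limits under-detection. It does not fix a frequency or make sampling equal across arms and centres.

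Three stronger readings are tempting, and the protocol supports none of them.

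- **That a patient without a blood gas is scored as having avoided severe ARDS.** No such rule is written. The only related rule counts treatment-arm drop-offs before evaluation as non-responders. The handling of patients without a gas may lie in an analysis plan not shown here.
- **That P/F at screening is also left to clinical indication.** P/F appears in inclusion criterion 4a and exclusion criterion 5a, and eligibility screening is a scheduled item, so a check of P/F is implied.
- **That the bias favours plasma.** The one instruction on unequal monitoring would, if anything, detect more ARDS on plasma and work against it. A team confident in plasma might instead sample less. Either is possible.

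The detection rates are also unanchored: nothing in the protocol supports a particular gap between arms.

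**Conclusion.** The point holds in a limited form. A component of the primary outcome has no fixed post-randomisation measurement, allocation is known to those who decide when to measure, and only transfused patients are singled out for closer observation. Detection can therefore differ by arm, and the protocol contains nothing to prevent this or make it visible.

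Neither the direction nor the size can be derived from the protocol. Under the assumptions shown, a 10-point detection gap with half of events non-fatal nearly doubles the error rate on one side. A 20-point gap triples it, towards benefit or harm according to which arm is under-detected. With a quarter of events non-fatal, a 20-point gap has about the effect of the 10-point gap. Equal 70% detection costs about 8 points of power. These figures show sensitivity and do not predict what will happen. The mortality component is not affected.

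**What to change.** Add an oxygenation row to the schedule on days when vital signs are already due (0, 1, 3, 7, 14 and 28), identical in both arms while the patient is in hospital. Record SpO2, FiO2 or oxygen device, and PaO2 where a gas was drawn. Attach the day-28 window to the ARDS component explicitly. Pre-specify one rule, applied the same way in both arms, for classifying patients with no gas, using a fixed SpO2/FiO2 equivalent. Report by arm the number of gases and the type of measurement behind each classification, with a sensitivity analysis restricted to the scheduled readings, so that unscheduled sampling cannot drive that result.

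The cost is a few CRF fields at existing visits and a fuller definition of the component. No extra blood gas is needed and 226 per arm is unchanged. Two limits remain. SpO2/FiO2 misclassifies some patients, possibly not equally by arm because the unblinded team sets the oxygen. Episodes between scheduled visits can still be missed.

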4. Duration of respiratory support required
 - a. Duration of Invasive Mechanical Ventilation
 - b. Duration of Non-Invasive

5. Radiological improvement
6. Adverse events (AE) associated with transfusion
7. To measure the change in RNA levels (Ct values) of SARS-CoV-2 from RT-PCR [Time Frame: Days 0, 1, 3, and 7 after transfusion]
8. Correlation between Viral neutralization titer and Elisa antibody Assay
9. Correlation between titers in donor plasma and IgG titer on transfusion
10. Levels of bio-markers pre and post transfusion
11. Need of Vasopressor use
12. Pre and post transfusion antibody titers

Other Exploratory Endpoints

1. Cumulative incidence of serious adverse events during the study period: transfusion reaction (fever, rash), transfusion related acute lung injury (TRALI), transfusion associated circulatory overload (TACO), transfusion related infection
2. Rates and duration of SARS-CoV-2 PCR positivity (RT-PCR) from days 0 and if further available.

Analysis Plan

Baseline data about the demography, clinical presentations, ongoing medical therapy, and clinical history of participants in both arms will be collected and compared. Response to convalescent plasma will be coded as a binary outcome – based on whether the composite primary end point is met or not. Adverse events associated with infusion of convalescent plasma will also be descriptively summarized and compared with the adverse events experienced by participants receiving standard of care.

The objective response rate, defined as the proportion of participants successfully meeting the primary end points, will also be reported, along with a two-sided 95% confidence interval calculated using the Clopper-Pearson method.[45] This will be compared between the intervention and control groups.

Participants who drop off from the treatment arm prior to evaluation of post-intervention response will be considered as non-responders, regardless of the discontinuation reasons, and will be included in the intention to treat analysis. Comparison between group response rates will be analyzed and reported.

Study Procedures:

	Screen	Baseline	Intervention (Convalescent Plasma infusion)	Follow-up				
Day	-1 to 0	0	0	1	3	7	14	28
Pre-Intervention Screening								
Eligibility screening and Informed Consent	x							

Demographic and Medical history	x							
SARS-CoV-2 RT-PCR test for eligibility	x							
Pregnancy test	x							
ABO	x							
Study Intervention								
Symptom checking	x	x	x	x	x	x	x	x

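### Hospital stay and duration of respiratory support are raw durations that death cuts short, so a survival difference could bias their comparison between arms

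*Protocol*

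**What the plan says.** In the protocol's Secondary Outcomes, item 2 reads in full "Hospital length of stay". Item 4 is "Duration of respiratory support required", divided into "Duration of Invasive Mechanical Ventilation" and the non-invasive equivalent. Neither item says what a patient who dies contributes.

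The Sample Size section starts from mortality: "18% of patients would succumb to COVID-19 infections" under standard care. It continues: "We considered a relative effectiveness of 50% for sample size calculations". It then applies the same two figures to participants meeting the primary outcome: the treatment-group proportion "is assumed to be 0.18 under the null hypothesis and 0.09 under the alternative hypothesis". The Primary Outcomes section defines that outcome as a composite of severe ARDS and death from any cause by Day 28.

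The Analysis Plan covers the binary composite response, its confidence interval and adverse events. Its one rule for non-completers counts treatment-arm drop-outs as non-responders. That rule concerns the binary response and does not reach the durations.

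**The concern.** Hospital stay and ventilation both end at death. Taken as worded, an in-hospital death on Day 5 is a shorter stay than a recovery with discharge on Day 14. A shorter stay naturally reads as the better result; the protocol's own background, describing plasma in SARS, treats early discharge as the favourable outcome.

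That would matter little if deaths were rare or balanced. Here the planning figures make them common and unequal. Patients whom plasma saves leave the group with short, truncated durations and add whatever time they then spend in hospital or on support. The durations could then offset a real gain, or point against plasma while the primary outcome favours it. If plasma were harmful, they could flatter it.

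**Working it through.** **The plan's own figure.** For 0.18 against 0.09, two-sided alpha 0.05, power 0.80 and pooled variance (mean proportion 0.135):

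n = [1.96 × √(2 × 0.135 × 0.865) + 0.8416 × √(0.18 × 0.82 + 0.09 × 0.91)]² / 0.09² ≈ 225.1, which rounds up to 226 per group.

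This reproduces the stated size; power at 226 is 80.2%. Read as mortality, the rates mean 0.18 × 226 ≈ 41 deaths in control and 0.09 × 226 ≈ 20 on plasma.

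**Inputs.** Mortality of 0.18 and 0.09 comes from the Sample Size section. The protocol gives no length of stay, day of death or time on ventilation, so those below are assumptions, shown with ranges.

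**Length of stay, death ending the stay.** Let S be the survivors' mean stay and D the mean day of death, with no other effect of plasma. Take S = 14 and D = 7.
- Control: 0.82 × 14 + 0.18 × 7 = 12.74 days.
- Plasma: 0.91 × 14 + 0.09 × 7 = 13.37 days.
- Difference: +0.63 days, longer on plasma, although the only difference is fewer deaths.

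In general the shift is 0.09 × (L − D), where L is the stay of a saved patient.
- L = 14, D from 10 to 5: +0.36 to +0.81 days.
- L from 12 to 21, D from 5 to 14: from 0.09 × (12 − 14) = −0.18 to 0.09 × (21 − 5) = +1.44 days.
- Saved patients staying 24 to 28 days, D from 10 to 7: from 0.09 × (24 − 10) = +1.26 to 0.09 × (28 − 7) = +1.89 days.
- L = D = 14: zero.

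A cut in the treated survivors' stay of 0.63 / 0.91 = 0.69 days (0.69 / 14 ≈ 5%) cancels the first example.

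**Survivors only.** This does not repair the comparison, because survival is itself affected by treatment. If the other survivors stay 14 days and saved patients stay 24, the plasma survivors' mean is (0.82 × 14 + 0.09 × 24) / 0.91 = 15.0 days, against 14 in control.

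**If 0.18 and 0.09 are composite rates.** The mortality gap is then smaller. If half of the events are deaths (an assumption: 9% against 4.5%), the first example becomes 0.045 × 7 ≈ 0.3 days.

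**Invasive ventilation.** Count 0 days if never ventilated, and assume that all who die are ventilated, for Vd days. Let a share f of saved patients still need ventilation, for Vs days. The shift is 0.09 × (f × Vs − Vd). With Vd = 5 and Vs = 12:
- f = 0: −0.45 days.
- f = 0.5: +0.09 days.
- f = 1: +0.63 days.

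The sign turns on whether plasma prevents intubation or only death on the ventilator.

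**Death-aware measure, first example.** Days alive and out of hospital to Day 28, death scored 0: 0.82 × (28 − 14) = 11.48 in control and 0.91 × (28 − 14) = 12.74 on plasma, a gain of 1.26 days. For a saved patient staying L days the contribution is 0.09 × (28 − L): 1.26 at L = 14, 0.36 at L = 24 and 0 at L = 28. It can be nil, but averted deaths alone cannot make it negative.

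**Detectability.** With an assumed SD of 6 to 8 days and 226 per arm, power to detect a 0.63-day shift is 20% to 13%; for 1.89 days it is 92% to 71%.

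**The case against.** The strongest reply is that the protocol states no analysis of these durations. It does not say that death ends the duration and it does not propose a survivors-only comparison. Handling of deaths in a secondary duration is commonly left to the statistical analysis plan, which is not at hand. That stands as far as the missing rule goes: its absence is not an error. It does not dispose of the point, because the variables the protocol itself names are ones that death shortens.

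A reader might infer that a life-saving effect would show up as harm. The documents do not support that. The +0.63 days requires plasma to halve deaths and change nobody else's stay, whereas the trial's hypothesis is a broader improvement in outcome. About a 5% shorter stay in treated survivors removes the shift, late deaths reverse it, and ventilation can move in plasma's favour. The 18% against 9% may also describe the composite rather than deaths.

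It is also fair that mortality sits in the primary outcome, so survival is seen first, and that a shift of 0.63 days would rarely reach significance. The larger shifts, with long stays in saved patients, would often be detected. Finally, the 1.26-day gain in hospital-free days is 0.09 × 14, all of it mortality, so the replacement partly repeats a primary component. That is a real cost, and a reason to keep the raw durations in view.

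**Conclusion.** The point holds as a possible bias, not a certain one. Length of stay and duration of invasive and non-invasive support are truncated by death, in a trial whose sample size assumes 18% mortality under standard care and a 50% relative reduction. A raw between-arm difference in them is therefore not interpretable alone.

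In the simple example the distortion is about 0.6 days. Over the assumed ranges it runs from about −0.2 to +1.9 days for stay, and from −0.45 to +0.63 days for invasive ventilation with 5 ventilated days before death and 12 in saved patients. All of these take 0.18 and 0.09 as mortality and shrink in proportion if they are composite rates. The primary analysis and the sample size are unaffected. The change is worth making because it is cheap and, in an open-label trial, is best settled before results are seen.

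**What to change.** For the between-arm comparison, define the outcomes as days alive and out of hospital to Day 28, days alive and free of invasive ventilation to Day 28, and the same for non-invasive ventilation. Score death by Day 28 as 0 and include all randomised participants. For hospital stay, time to discharge with death as a competing event is an acceptable alternative; in the first example it compares 82% with 91% discharged alive by Day 28. Keep the raw durations as descriptive tables beside mortality.

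The cost is mainly wording. The measures use discharge, ventilation and death dates that the existing outcomes already need, and follow-up already runs to Day 28. There are two drawbacks. The new measures combine duration with mortality, so they partly repeat a component of the primary outcome and should not be presented as independent support for it. Hospital-free days also need a stated rule for readmission before Day 28, which the Study Procedures schedule does not list as an item.

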For infusion of plasma existing SOP of the wards w.r.t transfusion of FFP should be followed with special care to monitor these patients during and post-24 hours of transfusion. All such transfusions have to be done using blood transfusion sets. The clinician will send a request for plasma component specifically mentioning the diagnosis and that convalescent plasma is required. An ABO compatible plasma bag of approx. 200ml will be issued maintaining all the blood bank records after thawing at 37 degree Celsius. the first plasma transfusion may be followed by one or two additional doses of 200 mL at 24 hours interval according to disease severity and tolerance of the infusions. The second plasma unit will preferably be from a different donor depending on the availability of another ABO compatible plasma unit or else plasma unit from the same donor will be issued.

Safety Assessments and Reporting

Definition of adverse events[45,46]

- Donor-related adverse events: They were divided into local reactions and systemic reactions. AEs were classified according to severity into mild, moderate, and severe and according to etiology in a donor into hypotensive reactions, citrate reactions, hematomas, loss of consciousness, seizures, and allergy.
- Kit/ Equipment-related adverse events: These are secondary to improper disposable sets. These are hemolysis, thrombus formation, air embolism, leakage, infection, improper mounting of the kits etc.
- Recipient related adverse events: A transfusion-related adverse reaction is a response or effect in a patient temporally associated with the administration of blood or blood components. Majority of the non-lethal and medically treatable adverse effects commonly associated with transfusion of plasma include transfusion related acute lung injury (TRALI); transfusion associated circulatory overload (TACO); allergic/anaphylactic reactions; transfusion related transmission of infections (TTI); febrile non-hemolytic transfusion reactions (FNHTR); hemolytic transfusion reactions (HTR); and rarely RBC allo-immunization

Details of Standard of care

The Ministry of Health and Welfare has issued detailed guidelines for the management of sCOVID-19 based on varying grades of severity.[47] For the management of ARDS or sepsis, the respective guidelines issued by ARDSNet and Surviving Sepsis campaign will be followed. Other institutional protocols for supportive management will be implemented.

Logistics of Investigational Products

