Indicative list of supplies/logistics necessary to conduct this study.

SI No	Item name
1	Anti-A
2	Anti-B
3	Anti-D
4	Antibody screen
5	Complete blood count
6	Serology (HIV, HBV, HCV, Syphilis & malaria)
7	NAT test (HIV, HBV & HCV)
8	Rapid IgG and IgM tests for COVID-19
9	IgM ELISA
10	IgG ELISA
11	Plasmapheresis disposable kit
12	Transfer bags
13	EDTA vials
14	Plain vials
15	20ml syringes
16	PPE kits
17	ELISA reader and washer
18	BBR-cum-freezer
19	Biosafety cabinet type 2
20	Donor Transport
21	Staff (technician / research associate)

Safety Assessments and Reporting

Definition of adverse event

An Adverse Event/Experience [AE] is any untoward medical occurrence in a participant undergoing TPE, is one which does not necessarily have a causal relationship with the TPE procedure. It can be any unfavorable and unintended sign, symptom, or disease, which is temporally associated with the use of convalescent plasma, whether or not considered to be causally related to convalescent plasma.

A Serious Adverse Event [SAE] is any untoward medical occurrence, at any point during convalescent plasma, results in:

- Death
- A life-threatening condition. This means any event in which the participant is at risk of death; it does not refer to a condition, which, with increasing severity, may result in death.
- Significant disability

Other medically significant outcomes, which may not result in any of the above, but may jeopardize the well-being of the participant, requiring greater degrees of medical or surgical interventions to prevent one of the outcomes listed above.

Data Management

Data Management Responsibilities

The Investigators will be responsible for assuring completeness, accuracy and timely collection of data. Case Record Forms (CRFs) should support the data entered in the electronic data capture system. They will be signed and dated by the person filling out the forms, and the investigator reviewing the same. Data will be reviewed by the Investigator and co-signed. Data management will be undertaken by ICMR-National Institute of Epidemiology.

Data Capture Methods

Paper CRFs will be used to collect data. The data will then be entered on an electronic system. A data entry system with electronic tracking, password restricted access, audit trail, with time and date stamps on data entry and edits, will be developed.

Types of Data

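### Exploratory endpoint 1 specifies serious adverse events by a list of transfusion events that conflicts with the protocol's own outcome-based SAE definition, so the reported SAE rate would be a mis-specified, partial measure.

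*Protocol*

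**What the plan says.** Under Other Exploratory Endpoints, item 1 is given as "Cumulative incidence of serious adverse events during the study period: transfusion reaction (fever, rash", and the list continues with "transfusion related acute lung injury (TRALI), transfusion associated circulatory overload (TACO), transfusion related infection". No seriousness criterion is attached to any item, and the protocol does not say whether the list is exhaustive.

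The second Safety Assessments and Reporting section, under Definition of adverse event, states: "A Serious Adverse Event [SAE] is any untoward medical occurrence, at any point during convalescent plasma, results in". The outcomes that follow are death, a life-threatening condition ("This means any event in which the participant is at risk of death") and significant disability. To these it adds other medically significant outcomes that "may jeopardize the well-being of the participant, requiring greater degrees of medical or surgical interventions to prevent one of the outcomes listed above".

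The recipient adverse events in the first Safety Assessments and Reporting section include TRALI and TACO and also "allergic/anaphylactic reactions; transfusion related transmission of infections (TTI); febrile non-hemolytic transfusion reactions (FNHTR); hemolytic transfusion reactions (HTR". The background section on convalescent plasma gives the same set.

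Elsewhere, 28-day all-cause mortality is part of the primary composite, and secondary outcome 6 covers adverse events linked to transfusion, without a restricted list. The Analysis Plan compares adverse events after plasma with those under standard of care. The schedule of procedures marks adverse event monitoring from the infusion to day 28.

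**The concern.** Safety is part of the stated primary objective, and exploratory endpoint 1 is the only listed endpoint that reports serious adverse events as such. It describes them by type of event, while the definition describes them by outcome. An event can satisfy one description and not the other, in either direction.

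An SAE incidence built from the list could not be reconciled with SAEs classified under the definition. Sites would have to decide for themselves whether a simple febrile reaction is serious, and whether an anaphylactic reaction belongs in the count. Every listed item follows from a transfusion, so the endpoint also fails to supply the contrast with standard of care that the Analysis Plan promises for adverse events.

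**Working it through.** The endpoint has no stated figure to reproduce, so the check is a comparison of text.

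| Event | Under the SAE definition | Under exploratory endpoint 1 |
|---|---|---|
| Uncomplicated fever or rash after infusion | Meets no criterion | Named, with no qualifier |
| TRALI, TACO, transfusion-related infection | Serious if an outcome criterion is met | Named, with no qualifier |
| Anaphylactic or haemolytic reaction | Serious if life-threatening or medically significant | Unclear: covered only if fever and rash are mere examples |
| Life-threatening or disabling event unrelated to transfusion | Serious, subject to the time clause | Not named |
| Death | Serious, subject to the time clause | Not named |

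**Step 1, too broad.** Fever and rash are the only examples given for a transfusion reaction, and on their own they meet none of the four outcome criteria.

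**Step 2, too narrow.** Death is the first outcome criterion and is absent from the list, as is every serious event that does not arise from a transfusion.

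**Step 3, control arm.** All four listed items need a transfusion. A control patient, who gets no study plasma, could have one only if transfused for another reason. The between-arm difference in this endpoint therefore largely reflects who was transfused.

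**Step 4, the definition has its own gap.** Its time clause ties an SAE to plasma treatment. Read literally, a control patient's death, or a treated patient's death well after infusion, is not plainly an SAE. Replacing the list with the definition is therefore not enough unless this clause also changes.

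**Scale only.** Inputs from Sample Size are 226 per arm and rates of 0.18 (control) and 0.09 (treatment). The 226 is reproduced by the two-sided pooled Z test at alpha 0.05 without continuity correction (power 0.8015), and nothing in this point alters it.

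- If the two rates are read as death rates, 0.18 × 226 = 40.7 and 0.09 × 226 = 20.3. About 41 control and 20 treated patients would die, and the list names death for none of them. The protocol also uses these rates for the whole composite; on that reading deaths could be fewer.
- The documents give no rate of febrile or rash reactions. If such reactions occurred in 1% to 10% of 226 recipients (an assumption), 0.01 × 226 = 2.3 and 0.10 × 226 = 22.6. That is about 2 to 23 events that need not meet the SAE definition.

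Neither line estimates the error in the reported rate.

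**The case against.** The strongest reply is that the governing term is serious adverse events, which the protocol defines, and that the list only names types of interest among events already judged serious. On that reading a trivial fever is not counted. The reading is possible, but the text does not state it, and offering fever and rash as the examples points the other way. It also leaves the endpoint limited to transfusion events.

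Several further objections stand and limit the point:

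- The endpoint is exploratory, and no sample size, test or primary result depends on it.
- Deaths are in the primary composite, and anaphylactic and haemolytic reactions fall under secondary outcome 6. Serious harm is not lost to the trial.
- If fever and rash are only illustrations, anaphylaxis and haemolysis may be included. Their status is ambiguous; they are not expressly excluded.

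A reader might infer three stronger conclusions, which the documents do not support:

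- **That the endpoint fails to measure serious harm at all.** TRALI, TACO and transfusion-related infection are listed and can be serious.
- **That disease fever would dominate the SAE count.** Fever is a COVID-19 symptom and is followed under "Time to symptom resolution", but the endpoint lists it as a form of transfusion reaction. No document gives a rate of fever after infusion.
- **That all deaths in both arms are already SAEs which the endpoint discards.** The definition's time clause prevents that claim for control patients.

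A statistical analysis plan, if there is one, might settle coding details. It could not honour both definitions, because the protocol states each of them.

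**Conclusion.** The contradiction holds. The protocol uses one term with two definitions, and the exploratory endpoint followed as written would give a partial and mis-specified SAE incidence. It can include non-serious reactions, does not name deaths or non-transfusion events, leaves anaphylactic and haemolytic reactions uncertain, and cannot support a comparison between arms.

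The defect is confined to the reported SAE rate. Its size cannot be estimated from the documents, because they give no reaction rates and the protocol does not say how the list is to be applied. The conclusion rests on taking the list as the specification of the endpoint and on control patients receiving no study plasma. It does not depend on any assumed frequency of fever. The point is worth acting on because safety belongs to the stated objective and the repair is cheap.

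**What to change.** Reconcile the sections as follows.

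1. Define exploratory endpoint 1 as the cumulative incidence of any event meeting the protocol's seriousness criteria, regardless of cause, in both arms to day 28. Remove the parenthesis naming fever and rash.
2. In the SAE definition, replace the time clause tied to plasma treatment with the study period from randomization, so that the definition applies equally to control patients.
3. Report each recipient reaction from the recipient adverse event list separately under secondary outcome 6, with seriousness recorded for each event.

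No new visits are needed, since adverse events are already monitored to day 28. The cost is wording changes to the protocol and CRF. The downside for the sponsor is an SAE count that may look less favourable, because it will include deaths.
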